1.5. Sample Size Determination

A sample size of 60 subjects per group is estimated to give approximately 90% power to detect a 2 point improvement relative to placebo in total Mayo score at all three doses, under the following assumptions:

- Hochberg step-up procedure adjustment for multiple comparisons (2-sided tests)
- Family-wise type 1 error rate to be controlled at 5%
- Residual change standard deviation (SD) of 3 points

The estimated power to detect a 2-point improvement relative to placebo for at least one of the three doses is greater than 98%.

Assuming a slightly larger residual change SD of 3.5 points, the estimated power to detect a 2 point active dose group vs. placebo improvement in total Mayo score at all three doses was approximately 73% and the estimated power to detect a 2 point improvement at one or more of the doses was approximately 94%.

Estimates were obtained using East software, with 10,000 simulations per case.

2. ANALYSIS SETS

Table 3: Analysis Sets

Analysis Set	Definition	Treatment Assignment
Screen Failures	Subjects who give informed written consent but are not randomized are considered screen failures. Screen failure subjects and the main reason for screen fail will be captured in the EDC.	N/A
Safety*	The Safety analysis set will include all subjects who received at least one dose of study drug (TD-1473 or placebo). The Safety analysis set is the primary analysis set for safety analyses.	Actual Treatment received (see Section 3.1.6)
ITT*	The Intent-to-Treat (ITT) analysis set comprises all randomized into the Phase 2b study.	Randomized treatment
Modified ITT*	The modified Intent-to-Treat (mITT) analysis set comprises all randomized subjects who receive at least one dose of study drug. The mITT set is the primary analysis set for efficacy summaries and analyses.	Randomized treatment
Modified ITT-16w*	The modified Intent-to-Treat for extended induction (mITT-16w) analysis set comprises all randomized into the Phase 2b study, who did not meet the criteria for clinical response by adapted Mayo score at Week 8, and, continued dosing during extended induction.	Randomized treatment
PP*	The Per-Protocol (PP) analysis set comprises all subjects in the mITT analysis set who complete their Week 8 visit and have no major analysis protocol deviations	Randomized treatment

- Due to confirmed data integrity violations the data for site 36044 (deviation report GCP-23) and site 38915 (deviation report GCP-11) will be excluded from all analysis sets.

3. STATISTICAL ANALYSES

3.1. General Considerations

All data from scheduled and unscheduled visits will be presented in the subject listings.

However, unless noted otherwise, only data from scheduled/windowed visits will be included in the summaries, statistical analysis, and calculation of derived parameters.

Summary tables and listings (e.g., post text tables and individual subject data listings are prepared according to ICH Guideline E3) include a “footer” providing explanatory notes.

Continuous variables will be summarized using an 8-point descriptive summary (number of subjects [n], mean, standard deviation [SD], median [Q2], interquartile range [25th percentile Q1, 75th percentile Q3], minimum, and maximum) unless otherwise indicated. Categorical variables will be summarized by frequency and percentage of subjects in each category. All summaries will be presented by treatment and visit when applicable.

For safety assessments, summary statistics will be reported by treatment.

Analyses and tabulations will generally be prepared using SAS®, version 9.4 or later.

3.1.1. Baseline Definition

In general, the baseline value for efficacy variables and for safety variables is the value associated with the last available pre first dose visit/time point at which the variable was to be collected according to the schedule of study procedures, and must have been collected predose.

The exceptions are for fecal samples and electronic tablet data that can be submitted within 3 days of first dose.

3.1.2. Study Day

If the date of interest occurs on or after the first dose/randomization date then study day will be calculated as (date of interest – date of first dose/randomization) + 1.

If the date of interest occurs prior to the first dose/randomization date then study day will be calculated as (date of interest – date of first dose/randomization).

There is no study day 0.

3.1.3. Visit Windows

All assessments (including unscheduled assessments) will be summarized using analysis windows. The exception is the End of Study 4 week follow up visit which will not be windowed.

The terminology of unscheduled will be applied to assessments that are outside an analysis window regardless of the nominal label associated with the assessments in the EDC system.

The following visit windows will be used in the summary of clinical data.

Table 4: Visit Analysis Windows

Nominal Visit	Nominal Day	Start (days)	Stop (days)
Screening	NA	-28	-1
Day 1	1	1	1
Week 2	14	7	21
Week 4	28	22	35
Week 8a/8b	56	46	Minimum of: 
 • Day 71, or • 8 Week Induction period end date
Week 12	Extended Induction day 28	Extended Induction day 22	Extended Induction day 35
Week 16	Extended Induction day 56	Extended Induction day 46	Minimum of: 
 • Extended Induction day 71, or • Extended Induction period end date

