- **Maintenance Week 0** (mWeek 0) if subject **achieved clinical response** (see Table 2 Maintenance Phase Schedule of Study Procedures)

Subject to be reminded not to take study drug on the morning of this next clinic visit, whether Week 8b or mWeek 0, to allow for re-randomization and initiation of study drug of either Extended Induction or Maintenance Study, whichever he or she qualifies for

- ² Week 8b, Week 12, and Week 16 visits pertain only to subjects who undergo extended induction (i.e., who do not demonstrate clinical response based on the adapted Mayo score from Week 8a visit)
- ³ Subject should be instructed not to take study drug from their Induction study drug bottles at home to allow for re-randomization and to receive the first dose of extended induction in the clinic.
- ⁴ Week 16 visit may be done over a period of 1 to 3 visits to complete: a) the Week 16 endoscopy, b) Week 16 clinical assessments (e.g., vital signs, weight, laboratory testing, and Quality-of-Life assessments), and c) an optional visit to bring subjects back (or could be done over the phone) to inform them that they should stop study drug and proceed to EOS visit if they did not achieve clinical response (those who achieve clinical response will proceed to mWeek 0 visit). [REDACTED]
- ⁵ Early Study Drug Discontinuation visit is for subjects who prematurely discontinue the Study drug during the Induction Study. Visit to be conducted within 5 days of the last dose of Study drug, if possible. Subject will also return for the EOS visit for collection of safety data and assessment of disease activity four weeks after last study drug. An EOS visit will be required for all subjects 4 weeks following their last dose of study drug, regardless if they completed the full duration of study drug treatment.
- ⁶ Seven-day window provided to allow time to receive results from the central reading of endoscopy performed at Week 8a.
- ⁷ Blood pressure and heart rate will be measured after the subject has been resting for at least 5 minutes in the seated or supine position. Vital sign measurements should be obtained prior to scheduled blood draws.
- ⁸ Obtain blood pressure and heart rate any time pre-dose at all visits and approximately 1-hour post-dose (any time ≥ 1 hour and < 2 hours) on Day 1 only.
- ⁹ ECGs should be performed after the subject has been resting in a supine position for at least 10 minutes.

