3.7.3. Additional Safety Assessments

3.7.3.1. Clinical Laboratory Parameters

Laboratory data, hematology, serum chemistry and urinalysis, will be summarized in terms of observed values and changes from baseline for induction period and overall. In addition, changes from baseline relative to normal ranges from the central lab (e.g., shifts from normal to abnormal high/low) will be summarized.

Summaries for laboratory parameters of special interest will also be presented, these will include:

- Neutrophils
- Leukoocytes
- Lymphocytes
- Hemoglobin
- Lipids [LDL cholesterol, HDL cholesterol, Cholesterol, and Triglyceride]
- Liver Function Test's [ALT, AST, Bilirubin]
- Creatinine
- Creatinine Kinase

The number and percentage of subjects with clinically abnormal lab values will also be summarized by timepoint for the following criteria:

- absolute neutrophil count of $< 1.0 \times 10^9/L$
- white blood cell count of $< 2.0 \times 10^9/L$
- absolute lymphocyte count of $< 0.5 \times 10^9/L$

A summary of maximum National Cancer Institute Common Terminology Criteria for Adverse Events (NCI-CTCAE) toxicity grade (Appendix 5.8) for postbaseline laboratory values through Week 8 and through Week 16.

Listings will flag laboratory values that are outside of normal range.

A listing of all abnormal lab values will be provided. Listings of subjects with any abnormal postbaseline laboratory values of CTCAE grade ≥ 2 will also be provided.

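### Phase 2b SAP analysis windows have gaps and no Early Discontinuation row, so gap-dated laboratory, vital-sign and ECG records miss the by-visit safety tables

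*SAP*

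**What the plan says.** - **Windows.** Phase 2b SAP 3.1.3, Table 4, assigns Day 1 to itself, Days 7–21 to Week 2 and Days 22–35 to Week 4. The next row begins at Day 46 ("Week 8a/8b 56 46") and closes at the earlier of Day 71 and the end of Induction. Week 12 covers "Extended Induction day 22 Extended Induction day 35". Week 16 opens at "Extended Induction day 46".
- **Exemption.** One visit is excused from windowing: "The exception is the End of Study 4 week follow up visit which will not be windowed". Early Discontinuation has neither a row nor an exemption.
- **Label.** "The terminology of unscheduled will be applied to assessments that are outside an analysis window regardless of the nominal label".
- **Consequence.** SAP 3.1 says that, unless noted otherwise, "only data from scheduled/windowed visits will be included in the summaries, statistical analysis, and calculation of derived parameters". All data, unscheduled included, go to listings.
- **Tables affected.** SAP 3.7.3.1: "The number and percentage of subjects with clinically abnormal lab values will also be summarized by timepoint for the following criteria". The criteria are neutrophils < 1.0, white cells < 2.0 and lymphocytes < 0.5 (×10⁹/L). SAP 3.7.3.3 presents the ECG and QTcF categories by visit and time point.
- **The visit concerned.** Protocol Table 1, footnote 5: "Early Study Drug Discontinuation visit is for subjects who prematurely discontinue the Study drug during the Induction Study". It is to take place within 5 days of the last dose if possible. Table 1 schedules chemistry, haematology, lipids, vital signs and ECG at it.
- **Protocol rule.** Section 8.8 lists unscheduled quantitative data without summarising them. It keeps unscheduled categorical data, with ECG finding categories as its example, in summaries covering the whole treatment period.

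**The concern.** A discontinuation visit can fall on any study day, including one that no window covers. Its results then count as unscheduled and leave the by-visit tables. The subjects concerned are those who stopped drug, so the loss need not be balanced across arms.

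ECG is the clearest case. Apart from Screening, Protocol Table 1 schedules it at Day 1, Week 8a, Week 16, Early Discontinuation and End of Study, and End of Study comes four weeks after the last dose. For a subject who stops before Week 8a, the discontinuation ECG is normally the only scheduled post-baseline ECG close to treatment. The same holds for a placebo subject who moves to 80 mg at Week 8b and stops before Week 16.

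**Working it through.** The documents state no count of unmapped days, so there is no figure to reproduce. The check is a direct count against Table 4, followed by a trace of where an out-of-window record can still appear.

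**1. Unmapped days, out of 56 in each period**

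| Period | Windows | Gaps | Count |
|---|---|---|---|
| Induction | 1; 7–21; 22–35; 46 onward | 2–6 and 36–45 | 5 + 10 = 15 (26.8%) |
| Extended Induction, day 1 counted as the Week 8b visit | 22–35; 46 onward | 2–21 and 36–45 | 20 + 10 = 30 (53.6%) |
| Extended Induction, strict reading of Table 4 | 22–35; 46 onward | 1–21 and 36–45 | 21 + 10 = 31 (55.4%) |

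**2. On-time scheduled visits**

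The protocol visit windows were applied to the Table 4 nominal days:
- Week 2 (±3): days 11–17
- Week 4 (±3): days 25–31
- Week 8a (−3/+5): days 53–61
- Week 12 (−3/+5): Extended Induction days 25–33
- Week 16 (−3/+7): Extended Induction days 53–63

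All lie inside the analysis windows, and they still do if every day number is shifted by one. No on-time scheduled visit at these weeks falls in a gap.

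**3. Discontinuation visits**

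A subject whose last Extended Induction dose is on day L is seen on days L to L + 5. For L = 2 to 16 every possible visit day (2 to 21) is unmapped. In Induction the same is true for L = 36 to 40 (visit days 36 to 45).

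As an illustration, assume the last dose is uniform over days 1–55 and the visit is 0 to 5 days later with equal weight. That gives 55 × 6 = 330 equally likely combinations. The documents do not supply this distribution.
- Induction: days 2–6 receive 2 + 3 + 4 + 5 + 6 = 20 combinations and days 36–45 receive 10 × 6 = 60. So 80/330 = 24%.
- Extended Induction: days 2–21 receive 2 + 3 + 4 + 5 + (16 × 6) = 110 and days 36–45 receive 60. So 170/330 = 51.5%, or 171/330 = 51.8% on the strict count.

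The remaining visits fall in a window and are summarised.

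**4. Where a gap-dated record can still appear**

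- *By-timepoint neutrophil, white-cell and lymphocyte counts:* excluded under SAP 3.1 and 3.1.3, with nothing in 3.7.3.1 to the contrary.
- *By-visit ECG and QTcF categories:* excluded likewise. The SAP has no whole-period ECG table in which the Protocol 8.8 rule could operate.
- *By-visit vital-sign summaries:* excluded.
- *Maximum CTCAE grade through Week 8 and Week 16:* not stated. Its grade 3 cut-offs (SAP 5.8) equal the three laboratory thresholds, so it could capture those values, but the SAP does not say that it uses out-of-window records.
- *Listings:* retained, including abnormal laboratory values, CTCAE grade ≥ 2, and QTcF > 500 msec or increase > 60 msec.

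SAP Appendix 1 does not list the missing whole-period categorical summary as a change from the protocol.

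**The case against.** The strongest reply is that little is lost.

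- **Mapping.** SAP 3.1.3 begins by saying that all assessments, unscheduled ones included, are summarised through the windows. A discontinuation visit inside a window is therefore kept. This stands. A reader might infer that Early Discontinuation laboratory and ECG results as a class leave the safety summaries, but only gap-dated ones do.
- **Other tables.** Protocol 7.2 directs that the three blood-count thresholds, when met on two sequential reports, be reported as an AESI with drug stopped. Clinically significant laboratory and ECG findings must be recorded as adverse events. SAP 3.7.2 and 3.7.2.1 tabulate these without visit windows. This largely answers the worry about laboratory values that end treatment, and together with the open status of the CTCAE table it means one cannot say that results survive only in listings. It is weaker for ECG, because QTcF change is not among the events named in Protocol 7.1.4 and no worst-value ECG table exists.
- **Dose selection.** A reader might infer that the larger Extended Induction gap weakens it. The documents do not support that. Protocol 3.1 and 8.11 base dose selection on data to Week 8, and the Dose Selection Committee also receives unblinded listings of SAEs, discontinuations for adverse events and markedly abnormal laboratory values.
- **Protocol intent.** Protocol 8.8 deliberately keeps unscheduled quantitative data out of summaries. This stands, and it is a reason to leave the by-visit means alone. It does not cover categorical findings, which the same section retains.

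**Conclusion.** The gaps are exact: 15 of 56 Induction days, and 30 of 56 Extended Induction days (31 on the strict count). Under the SAP as written, laboratory, vital-sign and ECG records dated there are left out of the by-visit safety summaries. The Protocol 8.8 provision for unscheduled categorical findings is not carried through for ECG categories or threshold counts. For the maximum CTCAE grade table the SAP is silent.

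The number of subjects affected is unknown, because the documents give no discontinuation rate or timing; the 24% and 52% rest on an assumed even spread. That abnormality rates would be understated more in arms with more toxicity stops is possible, but nothing in the documents shows it. The Induction gaps bear on dose selection, and the Extended Induction gaps bear on the study-report safety tables. This is an inexpensive improvement, not a serious flaw in the safety analysis. It concerns the Phase 2b SAP only, since the Maintenance SAP (3.1) summarises by CRF visit.

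**What to change.** For safety parameters, add to the Phase 2b SAP a by-arm summary over any post-baseline record within the treatment period as defined in SAP 3.1.5 (to End of Treatment + 5 days, which accommodates an on-time discontinuation visit). It should cover the abnormal-value counts, maximum CTCAE grade and ECG/QTcF categories, and should state that unscheduled and Early Discontinuation records are used, in line with Protocol 8.8. This would also retain an abnormal in-window laboratory value that the latest-record rule in SAP 3.1.4 replaces with a later retest.

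Optionally, add an Early Discontinuation row to Table 4 for safety data only. Such a row would pool subjects with different lengths of exposure, so it should supplement the whole-period summary and not replace it. Leave the efficacy windows and the quantitative by-visit summaries unchanged.

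The cost is a short SAP edit and minor programming. Safety percentages may become slightly less favourable.

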3.1.4. Multiple Assessments

In general, if multiple, valid, non-missing observations exist at a visit or collection time point then records will be chosen based on the following:

- The record closest to the nominal time point in question.
 If 2 records are equidistant:
- The later record of the two visits.
 If 2 records with same date/time
- Average (generally applies to assessments done in triplicate).

There is a special rule for laboratory test results: if there are multiple valid records within the visit window for the same visit or time point, the record(s) with the latest collection time will be selected rather than the record(s) with collection time closest to the nominal time. The protocol states that:

Additional and repeat laboratory safety testing for the evaluation of abnormal results and/or adverse events during the study may be performed at the discretion of the investigator or upon request of the Sponsor. Repeat laboratory testing of abnormal potentially clinically significant or clinically significant results for Screening evaluation of the subject may be repeated at the discretion of the investigator.

Hence, the latest laboratory test result associated with a visit or time point will be selected for summarization. All results will be provided in listings.

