(or serious adverse event), as described in Section 7.1.1 (Adverse Event) and Section 7.1.2 (Serious Adverse Event).

Clinical laboratory abnormalities of concern may include, but are not limited to, the following where the investigator must recheck within 2-7 days, except for AST or ALT > 3x ULN where these need to be rechecked within 48-72 hours, as deemed appropriate by the investigator:

- clinically significant reduction in neutrophils or leukocytes or lymphocytes that may place subjects at higher risk for infection such as:
 - moderate or severe neutropenia (e.g., absolute neutrophil count of $< 1.0 \times 10^9/L$)
 - moderate or severe leukopenia (e.g., white blood cell count of $< 2.0 \times 10^9/L$)
 - moderate or severe lymphocytopenia (e.g., absolute lymphocyte count of $< 0.5 \times 10^9/L$)
- abnormal hepatic panel (AST or ALT > 3x ULN)
- an excessive decrease in creatinine clearance (e.g., a reduction by $\geq 50\%$ from baseline (baseline for this purpose is defined as creatinine clearance calculated for Day 1, predose activities))

Depending on the subject's baseline and individual scenario, the investigator should report as an AESI and stop study drug treatment if any of the below is seen:

- moderate or severe neutropenia (e.g., absolute neutrophil count of $< 1.0 \times 10^9/L$) on two sequential laboratory reports
- moderate or severe leukopenia (e.g., white blood cell count of $< 2.0 \times 10^9/L$) on two sequential laboratory reports
- moderate or severe lymphocytopenia (e.g., absolute lymphocyte count of $< 0.5 \times 10^9/L$) on two sequential laboratory reports
- a reduction by $\geq 50\%$ from baseline in creatinine clearance on two sequential laboratory reports
- Abnormal AST or ALT > 3x ULN on two sequential laboratory reports with bilirubin > 2x ULN on at least one of the two laboratory reports or international normalized ratio (INR) > 1.5 on at least one of the two reports (INR will be checked locally)
- AST or ALT > 5x ULN on two sequential laboratory reports at least 2 weeks apart
- AST or ALT > 3x ULN associated with signs or symptoms suggestive of acute liver injury (e.g., the appearance of fatigue, nausea, vomiting, right upper quadrant pain or tenderness, fever, rash, and/or eosinophilia [$> 5\%$])
- AST or ALT > 8x ULN on one laboratory report

Note: See [Appendix 10](#) for an algorithm of evaluating and managing subjects with ALT or AST > 3x ULN.

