8.8. Safety Analyses

Safety summaries for the Phase 2b Induction, Phase 3 Induction, and Phase 3 Maintenance studies will include all subjects who received at least one dose of study drug. This will include subjects who are randomized to TD-1473 doses not selected for continued evaluation in the Phase 3 studies.

Summaries will be provided by scheduled visit and time point or for the entire treatment period, as appropriate. Quantitative data collected at unscheduled times will be listed but will not be included in summaries. Categorical data collected at unscheduled times (e.g., ECG finding categories) will not be included in summaries by time point but will be included in summaries of findings during the entire treatment period.

Safety variables to be summarized include vital signs, adverse events, clinical laboratory results (hematology, chemistry, and urinalysis), and corrected QT interval (QTcF).

For the Phase 2b and Phase 3 Induction studies, the primary assessment period for all safety endpoints will be the first 8 weeks.

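### In the Phase 2b SAP, the latest-record rule for laboratory data lets a recovered recheck replace the abnormal value that prompted it, so the by-timepoint abnormality counts and shift tables tend to run low

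*SAP*

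**What the plan says.** Four rules in the Phase 2b SAP act together.

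- SAP 3.1.3: "All assessments (including unscheduled assessments) will be summarized using analysis windows". Table 4 sets the windows: Week 2 is Days 7-21, Week 4 is Days 22-35, and Week 8 runs from Day 46 to the earlier of Day 71 and the end of the induction period. An assessment outside every window is called unscheduled, whatever its label in the database.
- SAP 3.1: unless noted otherwise, "only data from scheduled/windowed visits will be included in the summaries".
- SAP 3.1.4: with several valid records at a visit, the general choice is the record closest to the nominal time. Laboratory tests are an exception: "the record(s) with the latest collection time will be selected rather than the record(s) with collection time closest to the nominal time". The section concludes that "the latest laboratory test result associated with a visit or time point will be selected for summarization", and also states: "All results will be provided in listings".
- SAP 3.7.3.1: "The number and percentage of subjects with clinically abnormal lab values will also be summarized by timepoint", with cut-offs of neutrophils < 1.0, white cells < 2.0 and lymphocytes < 0.5 x 10^9/L. The same section plans shifts against the normal range and a table of maximum CTCAE grade through Week 8 and through Week 16.

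On the protocol side, Section 7.2 lists abnormalities of concern for which "the investigator must recheck within 2-7 days", or within 48-72 hours for AST or ALT above 3x ULN. The sentence ends by leaving this to the investigator's judgement. Section 8.8 says: "Quantitative data collected at unscheduled times will be listed but will not be included in summaries".

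**The concern.** The three cut-offs counted in SAP 3.7.3.1 are the same values that Protocol 7.2 gives as examples calling for a recheck. The subject who crosses a counted threshold is therefore the one most likely to have a second draw a few days later, and under SAP 3.1.4 that second draw is the one summarized. If it has recovered, a valid breach disappears from a table that presents itself as the number of subjects with abnormal values.

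The reason that SAP 3.1.4 gives for the exception cites only the protocol text on discretionary repeats and screening repeats. It does not mention the Section 7.2 recheck. Invalid specimens are already dealt with in SAP 5.2.3, so the exception acts on genuine results.

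Falls in neutrophils and lymphocytes, and changes in liver tests, are named in Protocol 1.5 as seen with a systemic JAK inhibitor. Protocol 8.11 makes safety the third step of dose selection and gives the committee unblinded summary tables. An arm with more transient breaches has more of them to lose, so the difference between arms in these counts can shrink.

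**Working it through.** The plan states no figure here, so the check is a count of days followed by a comparison of rules.

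**Inputs.** Visit windows from Protocol Table 1: Week 2 and Week 4 nominal day +/-3, Week 8a -3/+5 days, Week 8b or mWeek 0 1-7 days after Week 8a. Recheck lags from Protocol 7.2: 2-7 days, or 2-3 days for AST/ALT. Analysis windows from SAP Table 4. Assumption: every permitted day and lag has equal weight.

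**Condition.** The recheck is in the same window as the triggering value when visit day + lag <= last day of the window.

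**Week 2** (visit Days 11-17, window ends Day 21):
- Days 11-14: all 6 lags fit, 4 x 6 = 24.
- Days 15, 16 and 17: 5 + 4 + 3 = 12.
- Total 36 of 7 x 6 = 42, or 86%.
- AST/ALT: the latest case is Day 17 + 3 = Day 20, so 14 of 14.

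**Week 4** (visit Days 25-31, window ends Day 35): the same pattern, 24 + 12 = 36 of 42 (86%), and 14 of 14 for AST/ALT.

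On the nominal day itself, all 6 lags stay inside at both visits.

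**Week 8** (laboratory draw at Week 8a, Days 53-61). If the window ran to Day 71, every recheck would be inside, since 61 + 7 = 68. If it closes on a Week 8b or mWeek 0 visit g days after Week 8a (g = 1 to 7), with pre-dose draws that day still counted, the condition becomes lag <= g:
- Lags 2-7: 0 + 1 + 2 + 3 + 4 + 5 + 6 = 21 per visit day; 9 x 21 = 189 of 9 x 7 x 6 = 378, or 50%.
- Lags 2-3: 0 + 1 + 5 x 2 = 11 per visit day; 9 x 11 = 99 of 126, or 79%.

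Footnote 29 of Table 1 also allows the Week 8 laboratory draw at the Week 8b or mWeek 0 visit itself. A recheck after that visit's dose is outside the window, so the share can be lower still.

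**What the alternatives would keep.** Under the SAP's general closest-to-nominal rule (ties to the later record), the triggering value would stay in 27 of the 36 same-window cases at Week 2 and 27 of 36 at Week 4. Under Protocol 8.8, an unscheduled recheck would not be summarized and the scheduled value would stay in all of them.

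**How many breaches recover.** The documents give no figure. As an illustration only, take the first and second values as bivariate normal with 1-3% of first values below the cut-off. The share back above it on the second draw is 65-73% at a within-subject correlation of 0.7, 55-62% at 0.8 and 40-46% at 0.9. With 60 subjects per arm, 1-3% is 0.6-1.8 subjects per arm per visit.

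**Window gap.** SAP Table 4 leaves Days 2-6 and Days 36-45 in no window. Protocol Table 1 draws chemistry and hematology at the Early Study Drug Discontinuation visit. On those days the results become unscheduled under SAP 3.1.3 and leave the by-visit summaries under SAP 3.1.

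**The case against.** The strongest reply is that nothing is hidden. All results are listed, SAP 3.7.3.1 adds a listing of subjects with any post-baseline grade 2 or higher value, and Protocol 8.11 gives the Dose Selection Committee unblinded listings of markedly abnormal laboratory values. Clinically significant abnormalities are recorded as AEs, and laboratory abnormalities of concern form an AESI category with its own table. All of that stands, and it limits the harm. It does not repair the laboratory tables, because a listing gives no rate per arm.

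Several stronger readings are tempting, and the documents do not support them.

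- A reader might take the maximum CTCAE grade table to be affected as well. SAP 3.7.3.1 describes a maximum over post-baseline values in a period, which can be read as using all of them; SAP 3.1 and 3.1.4 do not exempt it. It is unclear. This matters most for AST and ALT, which are not among the three by-timepoint cut-offs.
- A reader might suppose that rechecks usually follow a stop in dosing, which would make recovery more likely. The documents do not say so. Protocol 7.2 mostly ties stopping to two sequential abnormal reports, so many rechecks would be drawn on treatment.
- A reader might infer that the effect runs strictly one way. It does so mainly. A draw prompted by an adverse event can also replace a normal scheduled value with an abnormal one.
- A reader might treat every recheck as compulsory. The protocol leaves it to the investigator's judgement.
- A reader might use the bivariate normal figures as the loss of a drug signal. They describe regression to the mean; a sustained effect would be confirmed more often and so stay counted.

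It can also be said that the rule is stated openly in SAP 3.1.4, and that SAP Section 1 does not treat the appendices as a formal part of the signed plan. So the omission from Appendix 5.1 is a minor matter of record beside the effect on the counts.

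**Conclusion.** The point holds for the Phase 2b SAP. The Maintenance SAP summarizes by CRF visit, has no latest-record rule and is not affected. At Week 2 and Week 4 a recheck within the protocol's time limits shares the window of the value that prompted it in 86% of permitted combinations, and in all of them for AST/ALT. At Week 8 the share is lower once the Week 8b or mWeek 0 dose closes the window. A breach is lost only when the recheck falls in the same window and no longer meets the criterion; a confirmed abnormality stays counted. The tables certainly exposed are the by-timepoint cut-off counts, the shift tables and the other by-visit laboratory summaries. They tend to understate abnormalities per arm, by a number that the documents do not allow one to state and that is likely to be small in absolute terms with 60 subjects per arm. The percentages rest on equal weight for each day and on rechecks being drawn within the protocol's limits. The uncovered days are a separate, smaller gap in the same summaries.

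**What to change.** In Phase 2b SAP 3.1.4 and 3.7.3.1:

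1. For abnormal-value counts, shift tables and maximum CTCAE grade, use the worst post-baseline value among all valid records in the window or period, scheduled and unscheduled. State this for the maximum-grade table explicitly.
2. Include Days 2-6 and 36-45 in the period-level summaries, so that early-discontinuation results on those days are counted.
3. For descriptive by-visit statistics, apply the SAP's general closest-to-nominal rule, with a retest replacing a result only when the first sample is invalid.
4. List the departure from Protocol 8.8 in Appendix 5.1. Counting unscheduled values in the abnormality tables is itself such a departure and should be recorded as deliberate.

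No new data are needed. The cost is a derivation flag, some table programming and slightly higher abnormality counts.
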